6.1 CRITERIA FOR SUBJECT ELIGIBILITY

Patients who have undergone T cell depleted allogeneic hematopoietic stem cell transplantation at MSKCC for:

1. De novo myelodysplastic syndromes (MDS): IPSS-1 with poor risk cytogenetics or higher IPSS.
2. Acute myelogenous leukemia (AML) in first remission that required more than 1 cycle of treatment to achieve remission or with the following cytogenetic abnormalities: FLT3 mutation, deletion/monosomy of chromosome 5 or 7, MLL gene rearrangement, or more than or equal to 3 cytogenetics abnormalities. Also patients in second or greater remission.
3. Patients with Secondary MDS/AML.
4. Patients will be considered eligible for the study if after transplant they achieved hematologic (<5% blasts) and cytogenetic remission.
5. Patients will be eligible to enter the study between 60-120 days post transplant.

6.2 Subject Inclusion Criteria

1. Age: pediatrics and adults patients – 1 year old-75 years old.
2. Karnofsky performance status >=60% for patients >16yo and Lansky performance status >=60% for patients ≤16yo
3. Stable blood counts (ANC>1000/uL, Hb>8gr/dL, Plt>50,000/ uL) not supported by transfusions.
4. Renal: Serum creatinine <1.5 ULN
5. Hepatic: <3xULN ALT and <1.5 total serum bilirubin, unless there is congenital benign hyperbilirubinemia.
6. Cardiac: Adequate cardiac function measured by LVEF>50%. If asymptomatic, pre-transplant echocardiogram is adequate. If symptomatic, echocardiogram needs to be repeated.
7. Each patient must be willing to participate as a research subject and must sign an informed consent form.

Patients who were treated with 5'-azacitidine without response prior to transplant would be eligible to participate on this protocol.

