1.0 PROTOCOL SUMMARY AND/OR SCHEMA

[figure not shown]
This is a single arm phase II trial to assess the efficacy of 5'-azacitidine to reduce the high relapse rate after T cell depleted (TCD) hematopoietic stem cell transplant (HSCT) from histocompatible matched or mismatched related or unrelated donor for patients with Myelodysplastic syndrome (MDS) and Acute Myelogenous Leukemia (AML) who are at high risk for relapse. Candidates for this trial will include MDS patients who have an International Prognostic Scoring System (IPSS) Intermediate-1 with poor cytogenetics and higher IPSS as well as AML patients with high risk cytogenetics and molecular mutations who on day +28-30 post T cell depleted transplant and prior to enrollment are in remission with no evidence of excess blasts or cytogenetics and/or molecular abnormalities.

Hematopoietic stem cell donors for this trial will include individuals who are 10/10 HLA matched and up to two-antigen mismatched at the HLA A, B, C DRB1 and DQB1 loci, as defined by high-resolution methods. The stem cell source can be either PBSC or bone marrow.

Patients will be prepared for transplantation with a chemotherapy only myeloablative regimen or a total body irradiation (TBI)-containing myeloablative regimen.

Maintenance therapy with 5'-azacitidine will be given at a dose of 32 mg/m²/day for 5 consecutive days subcutaneously, every 28 days (a cycle). This treatment can start between 60-120 days posttransplant depending on patient's clinical and hematological status and will be given for up to a year post transplant.

The primary endpoint of the study is the relapse rate after treatment initiation. Patients will also be monitored for regimen related toxicities, incidence of infections, incidence and severity of acute and chronic graft versus host disease (GvHD), marrow and T cell chimerism and characteristics of immune reconstitution. Correlative studies will look at the effects of DNA methylation and relapse risk in response to treatment with 5'-Azacitidine, the effect of maintenance 5'-azacitidine on expression of cell markers that are highly specific and sensitive for the detection of residual MDS/leukemic cells as well as the effect of treatment with 5'-Azacitidine on augmenting GVL by increasing regulatory T cells.

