8.1 PRETREATMENT EVALUATION

The patient will undergo comprehensive medical evaluation after stable engraftment has been documented. This evaluation includes:

1. Complete physical exam and medical history
2. Bone marrow tests post HSCT will be performed to determine remission status by morphology, cytogenetics and molecular studies (if indicated) and chimerism as part of routine post transplant assessments. At the same time, bone marrow sample will also be taken for baseline correlative studies under the biospecimen protocol. Any bone marrow sample collected prior to starting treatment with Azacitidine can be used as baseline for correlative studies.
3. Complete blood counts (CBC)
4. Complete metabolic panel
5. Pregnancy test will be checked for women at child bearing age prior to initiation of treatment

6. Cardiac: Adequate cardiac function measured by LVEF>50%. If asymptomatic, pre-transplant echocardiogram is adequate. If symptomatic, echocardiogram needs to be repeated.

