9.1 TREATMENT/INTERVENTION PLAN

1. 5'-azacitidine will be given at a dose of 32mg/m² for 5 consecutive days subcutaneously. Treatment will be given every 28 days (cycle). Treatment will be given up to a year post transplant.
2. CBC will be checked weekly during the first 2 cycles, and if stable every 2 weeks with following cycles. CBC results from tests performed externally will be accepted for Days 8, 15, and 22 of C1 and C2 and Day 15 of subsequent cycles. Comprehensive metabolic panel will be checked at the beginning of every cycle.
3. Pregnancy test will be checked for women at child bearing age prior to start of each cycle.
4. Bone marrow studies (day 100, and 6, 12, 18 and 24 months post transplant) for assessment of disease status and chimerism. Peripheral blood chimerism status at day 100, and 6, 12, 18 and 24 months post transplant will be tested as part of routine post transplant evaluation
5. Peripheral blood lymphocytes phenotyping and in-vitro response to standard panel of mitogen will be assessed as part of routine post transplant assessment
6. Bone marrow samples for correlative studies will be tested at the same time that patients are undergoing routine BM studies. These tests are considered experimental.
7. Peripheral blood samples for correlative studies will be collected prior to start of Azacitidine treatment on C1D1 and at 12 and 18 months post transplant. These tests are considered experimental.

Dose modifications

Event	Modification
ANC <1000/uL for > 4 days.	Drug held until resolved (ANC 1500) and up to 60 days. If after 60 days there is no neutrophils recovery the treatment will be permanently discontinued.
• If by next cycle ANC is 1000-1500, not G-CSF dependent	Resume therapy with 50% dose reduction
• If by next cycle ANC fully recovered, >1500 not G-CSF dependent	Resume full therapy dose
Platelets <10,000/uL for > 4 days, or if transfusion dependent to keep count>10,000/ uL	Drug held until resolved (>50,000) and up to 60 days.

• If by next cycle Platelets are 10,000-50,000, not transfusion dependent	Resume therapy but with 50% dose reduction
• If by next cycle Platelets >50,000	Resume full therapy dose
Hemoglobin < 8g/dL for > 4 days or if transfusion dependent	Drug held until resolved (> 8g/dL) and up to 60 days.
• If by next cycle hemoglobin >8g/dL	Resume full therapy dose
Hepatic toxicity – Drug related grade 3-4	Drug stopped

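### The entry blood-count criterion bars transfusion support but not G-CSF support, although the plan does not accept a G-CSF-dependent ANC as recovery after a hold

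*Combined protocol and SAP*

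**What the plan says.** **Entry.** Section 6.2, item 3, asks for "Stable blood counts (ANC>1000/uL, Hb>8gr/dL, Plt>50,000/ uL) not supported by transfusions". Sections 6.1, 6.3 and 8.1 and the assessment schedule in Section 10.0 contain no G-CSF restriction and no washout.

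**After an ANC hold.** The dose-modification table in Section 9.1 holds the drug when ANC is below 1000/uL for more than 4 days: "Drug held until resolved (ANC 1500) and up to 60 days". Two rows then govern resumption. The 50% dose applies "If by next cycle ANC is 1000-1500, not G-CSF dependent", and the full dose applies "If by next cycle ANC fully recovered, >1500 not G-CSF dependent".

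**Other lineages.** In the same table, transfusion dependence is itself a reason to hold, for platelets ("or if transfusion dependent to keep count") and likewise for haemoglobin.

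**Related safeguards.** Section 8.1 says "The patient will undergo comprehensive medical evaluation after stable engraftment has been documented". Section 6.3, item 6, excludes patients with neutrophil chimerism below 95% donor. Section 1.0 makes the start depend on the patient's "clinical and hematological status and will be given for up to a year post transplant". Section 9.1, item 2, says "CBC will be checked weekly during the first 2 cycles, and if stable every 2 weeks with following cycles".

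**Where it reaches the analysis.** G-CSF use is a secondary safety measure (Section 2.1, secondary objective 2) and is tabulated under Section 14.1. Grade III-IV neutropenia is one of the three stopping-rule events in Section 14.1.

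**The concern.** Item 3 is meant to establish that counts are good enough to begin a drug whose main expected toxicity is myelosuppression. It names one kind of support to exclude, and that kind bears on haemoglobin and platelets, not on neutrophils. The authors plainly regard G-CSF dependence as relevant to dosing, because they wrote it into both resume rows. Its absence at entry leaves the neutrophil criterion without the support condition that the other two counts have.

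Three things are at stake, all modest:

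- **Patient safety.** A patient whose neutrophils are not yet self-sustaining can qualify and start at full dose, 60 to 120 days after a T-cell-depleted transplant. Protection then rests on the investigator's judgement and on blood counts taken after dosing.
- **G-CSF tabulation.** Use carried over from before Cycle 1 Day 1 would be counted with use that follows azacitidine, unless it is dated.
- **Neutropenia stopping rule.** Such a patient has a different chance of registering a Grade III-IV event from other patients. It may be higher if marrow reserve is poor, or lower if continued G-CSF masks the drop.

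**Working it through.** **1. The text, step by step.**

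| Point in the plan | ANC | Platelets | Haemoglobin |
|---|---|---|---|
| Entry (6.2, item 3) | >1000/uL, no G-CSF condition | >50,000/uL, transfusion-free | >8 g/dL, transfusion-free |
| Hold trigger (9.1) | <1000/uL for >4 days | <10,000/uL for >4 days, or transfusion dependent | <8 g/dL for >4 days, or transfusion dependent |
| Resume at reduced dose (9.1) | 1000-1500, not G-CSF dependent | 10,000-50,000, not transfusion dependent | no such row |
| Resume at full dose (9.1) | >1500, not G-CSF dependent | >50,000, no support condition | >8 g/dL, no support condition |

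For platelets and haemoglobin, support is considered at entry and again as a hold trigger. For ANC it is considered only at resumption. A G-CSF-dependent ANC satisfies item 3 but neither ANC resume row.

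**2. The stopping boundary as stated.** Section 14.1 stops for neutropenia at 3 failures in the first 8 patients, 4 in 14, 5 in 20, 6 in 27, or 7 at any point, with N = 32. Let f(i, x) be the probability of having x failures after i patients without having stopped. Then

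f(i, x) = f(i−1, x)(1 − p_i) + f(i−1, x−1) p_i,

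and any mass that reaches the limit in force at patient i is moved to the crossing probability. With the same p for every patient:

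- p = 0.10 gives 0.0982 (the plan states 0.1).
- p = 0.30 gives 0.9238 (the plan states 0.92).

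The plan's figures reproduce.

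**3. Illustration with G-CSF-dependent entrants.** The documents give neither the number k of such patients nor their failure probability q, so both are assumptions. The other 32 − k patients have the drug rate d. The result is averaged over all possible entry positions of the k patients.

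| d | k | q | Probability of crossing | Baseline |
|---|---|---|---|---|
| 0.10 | 1 | 0.05 | 0.093 | 0.098 |
| 0.10 | 1 | 0.3 | 0.117 | 0.098 |
| 0.10 | 1 | 0.5 | 0.137 | 0.098 |
| 0.10 | 1 | 1 (extreme) | 0.185 | 0.098 |
| 0.10 | 3 | 0.05 | 0.084 | 0.098 |
| 0.10 | 3 | 0.3 | 0.163 | 0.098 |
| 0.10 | 3 | 0.5 | 0.241 | 0.098 |
| 0.30 | 1 | 0.05 | 0.911 | 0.924 |
| 0.30 | 3 | 0.05 | 0.880 | 0.924 |

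When q exceeds the drug rate, the boundary is crossed more often. When G-CSF masks neutropenia (q = 0.05), it is crossed less often, including at the 30% rate the rule is meant to detect.

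**4. Primary endpoint.** The relapse rule (7 or fewer relapses in 32) does not involve neutrophil counts. Its type I error is P(X ≤ 7 | 0.35) = 0.082 and its type II error is 1 − P(X ≤ 7 | 0.15) = 1 − 0.904 = 0.096. These agree with the stated 0.08 and 0.10 and do not change.

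**The case against.** The strongest reply is that entry and resumption ask different questions. The resume rows apply only after neutropenia has occurred on azacitidine, and a stricter test after demonstrated toxicity is ordinary practice. The thresholds already differ in this way: an unsupported ANC of 1000-1500 starts at full dose but resumes at 50%. G-CSF dependence is also not a hold trigger, so a treated patient kept above 1000/uL on G-CSF is never held. Nor is the support wording uniform for the other lineages, since the full-dose platelet row and the haemoglobin resume row carry no transfusion condition. Finally, several safeguards exist, the drug is given at low dose, and the number of affected patients could be zero.

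Much of this stands. The resume rows are not a general bar on dosing, the difference in thresholds is not a fault, and no effect on the trial's results has been shown. But none of it supplies the missing condition:

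- If stable counts already implied unsupported counts, item 3 would not need to name transfusions.
- Donor chimerism shows where neutrophils come from, not whether the count sustains itself.
- Stable engraftment is not defined with respect to G-CSF.
- Weekly counts in cycles 1 and 2 detect a problem only after the first dose.

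**Conclusion.** The concern holds as a minor, inexpensive improvement. Confidence is high that the condition is missing from the text. How much it matters in practice is unknown, because that depends on how many patients are still on G-CSF at days 60-120.

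The conclusion rests on the wording of Sections 6.2 and 9.1, not on the boundary illustration. That illustration shows only that one such patient would probably have a small effect of uncertain sign on the neutropenia rule, and that three could have a larger one if their failure probability were high. The G-CSF tabulation problem can be solved by dating use from the medical history and source records. Sample size, type I error and power for relapse are unaffected.

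**What to change.** Amend Section 6.2, item 3, so that the counts must be *not supported by transfusions or G-CSF*, and state a short G-CSF-free interval before enrolment, with its length set by the investigators. In Section 14.1, specify that the G-CSF tabulation counts new use after Cycle 1 Day 1. The stopping rule needs no change.

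The cost is a few words and one tabulation convention. The downside is a short delay, or the occasional loss, of a patient still on G-CSF within the day 60-120 window. That deserves some weight, since accrual is expected at 6-7 patients a year and Section 4.3 wants treatment to begin promptly, but the 60-day window leaves room for a brief washout.

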6.3 Subject Exclusion Criteria

Patients will be excluded from the trial if at time of enrollment:

1. Active uncontrolled bacterial, fungal or viral infection.
2. Evidence of uncontrolled graft-versus-host disease.
3. Pulmonary: new onset hypoxia
4. Known or suspected hypersensitivity to 5'-azacitidine or mannitol.
5. Evidence of residual disease either by increased blasts count (>5%) or persistence of previous known cytogenetics abnormalities.
6. Peripheral blood neutrophil chimerism: less than 95% donor.

7.0 RECRUITMENT PLAN

Patients who fulfill the eligibility criteria as listed in section 6.0 will be recruited for this study by an attending physician of the allogeneic BMT services in Medicine and Pediatrics. In the period of time between 60-120 days post-transplant, patients who are eligible for the study protocol will be offered to participate. A discussion will take place about the need for treatment with 5'- azacitidine which involves 5 days of subcutaneous injection every month for a year post transplant, the rational of decreasing risk of relapse, and the potential side effects, which at this part are mostly known to be related to myelosuppression and decreased blood counts. This protocol will take due notice of NIH/ADAMHA policies concerning inclusion of women and minorities in clinical research population.

8.1 PRETREATMENT EVALUATION

The patient will undergo comprehensive medical evaluation after stable engraftment has been documented. This evaluation includes:

1. Complete physical exam and medical history
2. Bone marrow tests post HSCT will be performed to determine remission status by morphology, cytogenetics and molecular studies (if indicated) and chimerism as part of routine post transplant assessments. At the same time, bone marrow sample will also be taken for baseline correlative studies under the biospecimen protocol. Any bone marrow sample collected prior to starting treatment with Azacitidine can be used as baseline for correlative studies.
3. Complete blood counts (CBC)
4. Complete metabolic panel
5. Pregnancy test will be checked for women at child bearing age prior to initiation of treatment

6. Cardiac: Adequate cardiac function measured by LVEF>50%. If asymptomatic, pre-transplant echocardiogram is adequate. If symptomatic, echocardiogram needs to be repeated.

9.1 TREATMENT/INTERVENTION PLAN

1. 5'-azacitidine will be given at a dose of 32mg/m² for 5 consecutive days subcutaneously. Treatment will be given every 28 days (cycle). Treatment will be given up to a year post transplant.
2. CBC will be checked weekly during the first 2 cycles, and if stable every 2 weeks with following cycles. CBC results from tests performed externally will be accepted for Days 8, 15, and 22 of C1 and C2 and Day 15 of subsequent cycles. Comprehensive metabolic panel will be checked at the beginning of every cycle.
3. Pregnancy test will be checked for women at child bearing age prior to start of each cycle.
4. Bone marrow studies (day 100, and 6, 12, 18 and 24 months post transplant) for assessment of disease status and chimerism. Peripheral blood chimerism status at day 100, and 6, 12, 18 and 24 months post transplant will be tested as part of routine post transplant evaluation
5. Peripheral blood lymphocytes phenotyping and in-vitro response to standard panel of mitogen will be assessed as part of routine post transplant assessment
6. Bone marrow samples for correlative studies will be tested at the same time that patients are undergoing routine BM studies. These tests are considered experimental.
7. Peripheral blood samples for correlative studies will be collected prior to start of Azacitidine treatment on C1D1 and at 12 and 18 months post transplant. These tests are considered experimental.

Dose modifications

Event	Modification
ANC <1000/uL for > 4 days.	Drug held until resolved (ANC 1500) and up to 60 days. If after 60 days there is no neutrophils recovery the treatment will be permanently discontinued.
• If by next cycle ANC is 1000-1500, not G-CSF dependent	Resume therapy with 50% dose reduction
• If by next cycle ANC fully recovered, >1500 not G-CSF dependent	Resume full therapy dose
Platelets <10,000/uL for > 4 days, or if transfusion dependent to keep count>10,000/ uL	Drug held until resolved (>50,000) and up to 60 days.

• If by next cycle Platelets are 10,000-50,000, not transfusion dependent	Resume therapy but with 50% dose reduction
• If by next cycle Platelets >50,000	Resume full therapy dose
Hemoglobin < 8g/dL for > 4 days or if transfusion dependent	Drug held until resolved (> 8g/dL) and up to 60 days.
• If by next cycle hemoglobin >8g/dL	Resume full therapy dose
Hepatic toxicity – Drug related grade 3-4	Drug stopped
Drug related grade 1-2	Next cycle delayed up to 60 days for resolution or reduced by 25% on subsequent cycles (resume full dose on next cycle once resolved)
Creatinine > 50% above age-adjusted ULN	Drug held
Creatinine ≤ 50% above age-adjusted ULN after a maximum delay of 45 days	Dose reduced 50% on next cycle (resume full dose on next cycle once resolved)
Serum bicarbonate level (CO2) - Unexplained reduction; < 20mEq/L	Dose reduced by 50% on next cycle
Cardiac, pulmonary, dermatologic, or neurologic toxicity - Drug related grade 3-4	Drug stopped
Acute infection	Drug held (resume full dose once resolved)

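### After a hold for low neutrophils or platelets, the dose-modification table's header rows and sub-rows give different instructions for the same count, and the protocol does not say which governs

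*Combined protocol and SAP*

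**What the plan says.** All the rules are in the dose-modification table of Section 9.1.

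- **Neutrophils.** The trigger is "ANC <1000/uL for > 4 days". The header row's action is "Drug held until resolved (ANC 1500) and up to 60 days", followed by permanent discontinuation if neutrophils have not recovered after 60 days. The first sub-row reads "If by next cycle ANC is 1000-1500, not G-CSF dependent", with the action "Resume therapy with 50% dose reduction". The second reads "If by next cycle ANC fully recovered, >1500 not G-CSF dependent", with full dose.
- **Platelets.** The trigger is a count under 10,000/uL for more than 4 days, or transfusion dependence to stay above that level. The header row's action is "Drug held until resolved (>50,000) and up to 60 days". The first sub-row reads "If by next cycle Platelets are 10,000-50,000, not transfusion dependent" and resumes at half dose; the second resumes full dose above 50,000.
- **Hemoglobin.** A single value, 8 g/dL, both ends the hold and allows resumption.

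Two other places matter. Section 4.3 expects 8-10 cycles per patient. Section 13.0 requires at least 4 cycles for evaluability. It treats patients who fall short because of treatment-related toxicity as evaluable for toxicity only, without replacement; patients who relapse before 4 cycles remain evaluable.

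**The concern.** Each header row defines numerically when the hold ends, and a sub-row then restarts the drug at counts that do not meet that definition. No sentence ranks one over the other. Two investigators could see the same patient with the same count and, each citing the protocol, one could keep holding while the other treats at half dose.

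Myelosuppression is the main risk that the recruitment discussion in Section 7.0 discloses, so this is first a safety rule. It also governs how many cycles a patient receives, and the number of cycles feeds the evaluability rule in Section 13.0.

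**Working it through.** The plan gives no figure to reproduce on this point. The check applies the header row and the sub-rows separately to a range of counts, then compares the possible ways of reading them together.

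**Step 1. Apply each row literally.** Inputs are the thresholds in the Section 9.1 table. The patient is already on a triggered hold, the next cycle is due, and there is no G-CSF or transfusion dependence. The header's ANC 1500 is taken to mean 1500 or above (an assumption).

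| Count per uL | Header row | Sub-rows | Agree? |
|---|---|---|---|
| ANC 900 | hold | none applies | yes |
| ANC 1000 | hold | half dose | no |
| ANC 1200 | hold | half dose | no |
| ANC 1499 | hold | half dose | no |
| ANC 1500 | resolved | half dose | boundary value |
| ANC 1501 | resolved | full dose | yes |
| Platelets 9,000 | hold | none applies | yes |
| Platelets 10,000 | hold | half dose | no |
| Platelets 30,000 | hold | half dose | no |
| Platelets 50,000 | hold | half dose | no |
| Platelets 50,001 | resolved | full dose | yes |

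The rows disagree from ANC 1000 to just under 1500 and from platelets 10,000 to 50,000 inclusive. They agree outside those ranges. Hemoglobin has no such conflict.

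**Step 2. Follow one count, ANC 1200 without G-CSF, under three readings.**

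| Reading | 1200 when the next cycle is due | 1200 first reached later, before day 60 |
|---|---|---|
| Header governs | hold | hold |
| Sub-rows govern whenever a cycle is considered | half dose | half dose |
| Sub-rows govern on the due date, header afterwards | half dose | hold |

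No two readings agree in both columns, and the text does not choose among them. At day 60 there is a further question. If recovery means 1500, a patient at 1200 is permanently discontinued; if it means 1000, that patient has recovered. The platelet row gives the same 60-day limit but does not state what follows when it expires.

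**Step 3. Consequence for the 4-cycle rule.** Cycles are 28 days apart. A 60-day window can contain at most three scheduled starts (for example days 2, 30 and 58). With 8-10 cycles expected, one hold of up to 60 days leaves at least 8 - 3 = 5 cycles, or 10 - 3 = 7, so a single hold followed by resumption need not take a patient below 4. Permanent discontinuation can: a patient held after cycle 1, 2 or 3 and then stopped has at most 3 cycles. The ambiguity in the word recovery could therefore decide evaluability for an early hold. The documents do not give the number of such patients.

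**The case against.** The best defence is the table's layout. The sub-rows are bullets under the header, they refer to the next cycle, and their action is to resume, so they presuppose the hold. On the third reading above they settle the decision on the due date, and the header threshold with its 60-day limit covers patients who have not qualified by then. Both sets of thresholds then have a purpose. This stands as a plausible reading, and a reader who inferred that the two instructions can never be reconciled would go too far. It does not remove the point: the protocol does not state this reading, it competes with the other two, and it leaves recovery at 60 days undefined.

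Four stronger inferences are tempting, and the documents do not support them.

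- *Any patient with ANC 1000-1500 or platelets 10,000-50,000 gets contradictory instructions.* The conflict needs a prior triggered hold and the absence of G-CSF dependence (neutrophils) or transfusion dependence (platelets).
- *The more-than-4-days trigger cannot be judged.* Section 9.1 says "CBC will be checked weekly during the first 2 cycles, and if stable every 2 weeks with following cycles", so two-weekly counts apply only to stable patients. Section 10.0 allows further tests when clinically indicated and more frequent visits. Consecutive low weekly counts would reasonably support a duration above 4 days, and transfusion dependence triggers the platelet and hemoglobin rows without any duration. What remains is a minor note: no repeat count is expressly required after a low value.
- *The cytopenia stopping boundaries in Section 14.1 are distorted.* The qualifying cytopenia comes before the choice to hold or resume. Nothing shows that the choice adds a patient not already counted, and the documents print no grade cut-offs that would settle it.
- *The trial's error rates are affected.* They depend only on 32 patients, the limit of seven relapses, and the 35% and 15% rates.

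**Conclusion.** The point holds as an unreconciled inconsistency within one table. After a triggered hold, ANC from 1000 to just under 1500 without G-CSF dependence, and platelets from 10,000 to 50,000 without transfusion dependence, are both held by the header row and restarted at half dose by the sub-row. For neutrophils at 60 days, the undefined recovery wording adds permanent discontinuation as a possible outcome.

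The effect is on patient safety and on cycles received. An effect on reaching 4 cycles is possible, chiefly through permanent discontinuation after an early hold, but its frequency cannot be estimated from the documents. The conclusion assumes that the table means what it literally says and that no other text ranks its rows; none was found. It should be corrected, but it is not a reason to question the design.

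**What to change.** Amend the Section 9.1 table so that each header row, its sub-rows and the 60-day wording agree, and every post-hold ANC and platelet value maps to one action at each decision time. In particular, the sponsor should:

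- state whether the sub-rows override the header threshold, and whether they apply only when the next cycle falls due or at any later time within the hold;
- define neutrophil recovery at 60 days by a stated count;
- state what follows when the 60-day platelet limit expires.

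Which thresholds and doses apply is for the sponsor and investigators to decide; this review proposes none. As a minor addition, the protocol could say how a duration above 4 days is judged from the available counts.

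The cost is a wording amendment, with no additional patients or procedures and no change to the statistical design.

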10.0 EVALUATION DURING TREATMENT/INTERVENTION

During the treatment patients will be seen in clinic every 4 weeks (prior to every cycle) and more frequently if required by primary BMT attending. All patients will be closely monitored and evaluated as per MSKCC BMT standard of care guidelines. Evaluations may be withheld if the treating physician feels that there is a strong contra-indication to perform the study (e.g. patient has relapsed or is terminally ill). Also, additional tests will be performed as clinically indicated. Study specific assessment schedule listed in table below.

Schedule of Study Assessments

Procedures	Pre-Treatment	Post Treatment Start					
		C1 & C2			C3+		
		D1	D8	D15	D22	D1	D15
Window	45	(+/-) 7	(+/-) 3	(+/-) 3	(+/-) 3	(+/-) 7	(+/-) 3
Eligibility	X						
Informed consent	X						
History/Physical	X						
Pregnancy Test (1)	X	X					X
Blood Chemistry/CMP (2)	X	X					X
CBC (2)	X	X	X	X	X	X	X
Echo- if no new symptoms, pretransplant is adequate	X						
Toxicity assessment (3)		X				X	
Correlative studies – Peripheral blood for Tregs expression studies (4)		X*					

Procedures	Post Transplant				
	100 days	6 months	12 months	18 months	24 months
Window	(+/-) 21	(+/-) 14	(+/-) 14	(+/-) 14	(+/-) 14
Chimerism (Peripheral Blood) (5)	X	X	X	X	X
Bone marrow aspirate and/or biopsy (6)	X	X	X	X	X
Peripheral blood lymphocytes phenotyping and in-vitro response (7)	X	X	X	X	X
Correlative studies - BM sample for methylation assays, flow studies for MRD (8)	X	X	X	X	X
Correlative studies – Peripheral blood for Tregs expression studies			X	X	

*Peripheral blood samples will be collected prior to start of Azacitidine treatment on C1D1 only

- (1) Pregnancy Test – Not required for Cycle 1 Day 1 if done at screening, but required for Day 1 of each subsequent cycle for FCBP.
- (2) CBC – checked weekly during the first 2 cycles, and if stable, every 2 weeks with subsequent cycles. Outside CBC results will be accepted for D8, 15 and 22 of C1 and C2 and for D15 of subsequent cycles. CBC/Chemistry must result prior to IP administration on or within 7 days of Day 1 of each cycle. If a CBC is performed within overlapping windows for two time-points, it is not necessary to repeat unless clinically indicated.

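### Transfusion dependence alone triggers the hemoglobin hold, but the full-dose resume row asks only for hemoglobin above 8 g/dL, so a dependent patient transfused above 8 g/dL meets both instructions

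*Combined protocol and SAP*

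**What the plan says.** The relevant text is the dose-modification table in section 9.1.

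- **Hold.** The hemoglobin event is "Hemoglobin < 8g/dL for > 4 days or if transfusion dependent". The two parts are joined by *or*, so dependence is enough by itself, with no hemoglobin value and no duration attached.
- **Release.** The action is "Drug held until resolved (> 8g/dL) and up to 60 days". The parenthesis gives a hemoglobin value and nothing else.
- **Resume.** There is one sub-row, "If by next cycle hemoglobin >8g/dL", and its action is full dose. There is no half-dose row for hemoglobin.

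Other places in the protocol do ask for counts that are not propped up:

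- Both ANC resume rows in the same table, half dose and full dose, require that the patient is not dependent on G-CSF.
- The half-dose platelet row reads "If by next cycle Platelets are 10,000-50,000, not transfusion dependent".
- Section 6.2, item 3, sets the same 8 g/dL hemoglobin threshold for entry and requires that the counts be "not supported by transfusions".

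The full-dose platelet row, "If by next cycle Platelets >50,000", has no such condition.

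**The concern.** A dosing table should give one instruction for one clinical state. Here the state is an ordinary one: a patient whose anemia needs regular transfusion and whose hemoglobin on the pre-cycle blood count is above 8 g/dL because of that transfusion. The hold row names this patient's dependence as a reason not to dose. The resume row, read as written, returns the same patient to full dose. Two clinicians who both follow the table could act in opposite ways.

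What is at stake is patient safety and consistency of exposure. Section 11.1 lists anemia among the likely effects of azacitidine. The early-termination boundaries in section 14.1 cover neutropenia, thrombocytopenia and treatment-related mortality, but not anemia, so the hemoglobin rows are the protocol's only explicit dosing rule for it. Transfusion frequency is also part of the second secondary objective (section 2.1). Inconsistent dosing of dependent patients would make that tabulation harder to interpret.

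**Working it through.** No sample size, power or event figure enters this point, and the plan states no figure to reproduce. The check is one of logic, followed by one line of arithmetic.

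**Inputs (all from section 9.1)**

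- Hold = (hemoglobin < 8 g/dL for > 4 days) OR (transfusion dependent).
- Resume at full dose = (hemoglobin > 8 g/dL by the next cycle).
- Dose = 32 mg/m² on each of 5 days per cycle.

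**Step 1. Apply both rules as written at the start of the next cycle.**

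| Patient state | Hold met? | Full-dose resume met? | Result |
|---|---|---|---|
| Below 8 g/dL for more than 4 days | Yes | No | Hold |
| Dependent, 7.5 g/dL for 2 days | Yes, by dependence | No | Hold |
| Dependent, exactly 8 g/dL | Yes, by dependence | No | Hold |
| Dependent, above 8 g/dL after transfusion | Yes, by dependence | Yes | **Both** |
| Not dependent, above 8 g/dL | No | Yes | Full dose |

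The conflict sits in one row. The dependence trigger still works at or below 8 g/dL. Above 8 g/dL, the resume row contradicts it.

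**Step 2. Look for a tie-breaker elsewhere.** Section 10.0 says "patients will be seen in clinic every 4 weeks (prior to every cycle" and calls for a toxicity assessment on or within 7 days of Day 1 of each later cycle. A blood count must also be available before dosing. Transfusions are to be tabulated (sections 2.1 and 14.1). Transfusion status would therefore usually be known. None of these passages makes it a condition for resuming. The entry criterion does, but it governs enrollment only.

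**Step 3. Size per affected cycle.** Full dose = 32 × 5 = 160 mg/m². With no intermediate tier, the two readings give 0 or 160 mg/m².

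**Step 4. Repeat step 1 with the qualifier added.** Resume = (hemoglobin > 8 g/dL) AND (not transfusion dependent). In the fourth row, resume becomes No and only the hold applies. The other four rows do not change.

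**The case against.** The best defense is that the resume row sits beneath the hold and should be read with it. What must resolve is the event, and the event includes dependence; a patient who is still dependent has not resolved. The neighboring rows support a relaxed reading of the parentheses. ANC is held to 1500, yet half dose resumes at 1000–1500. Platelets are held to above 50,000, yet half dose resumes at 10,000–50,000. The parenthesis may be shorthand and not a full definition.

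This is a plausible reading, and it rules out the stronger inference that the table plainly directs full dose for dependent patients. It does not remove the conflict, because the resume row states its own condition and again names only the hemoglobin value. Two defensible readings remain, and nothing in the text chooses between them.

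A second objection is that clinicians will know the transfusion status. They probably will, but knowing it does not tell them which instruction governs.

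A third is that dependence is itself undefined for hemoglobin: there is no threshold or time window, whereas the platelet row at least ties dependence to staying above 10,000. That stands. The qualifier settles which instruction applies to a dependent patient, but not who counts as dependent.

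A reader might also infer a larger problem from the 60-day limit. The ANC row ends with "If after 60 days there is no neutrophils recovery the treatment will be permanently discontinued", while the hemoglobin row names no action at day 60. It is tempting to conclude that dependent patients should be taken off treatment then, and to count the cycles lost as the size of this defect. The documents do not support that. The platelet row has the same silence, so the gap is not peculiar to hemoglobin. Stopping for persistent anemia would be a new clinical rule. Cycles lost under it, or under a correctly applied hold, would be costs of those rules and not effects of the missing qualifier.

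**Conclusion.** The point holds as an internal contradiction in the hemoglobin rows. A transfusion-dependent patient kept above 8 g/dL by transfusion meets both the hold and the full-dose resume instruction, a difference of 0 or 160 mg/m² for each affected cycle. How often this would occur is unknown, because the documents give no transfusion rates for this population.

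The conclusion rests on two assumptions: that *or* in the hold row makes dependence a sufficient trigger, and that the resume row means what it states. The comparison with the ANC rows, the half-dose platelet row and the entry criterion suggests an oversight, since no reason is given for treating hemoglobin differently.

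A reader might infer that the trial's statistical basis is affected. It is not: the 32 planned patients, the type I and II errors of 0.08 and 0.10, and the stopping boundaries do not depend on these rows. The correction should be made because it is safer and cheap, but the defect does not threaten the trial.

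**What to change.** Amend two cells of the section 9.1 table:

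- Resume row: *If by next cycle hemoglobin >8 g/dL, not transfusion dependent*.
- Hold row: *until resolved (>8 g/dL, not transfusion dependent)*.

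Adding the same qualifier to the full-dose platelet row is optional, for consistency only; a count above 50,000 is very unlikely in a patient who needs transfusion to stay above 10,000. A short definition of transfusion dependence for hemoglobin would help, but it is a clinical choice and is not needed to remove the contradiction.

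The cost is a short protocol amendment, with no new visits, data or planned patients. Some dependent patients will be held longer and may lose cycles, which matters because section 13.0 sets a minimum of 4 cycles for evaluability. What to do when a hold reaches 60 days should be decided separately and, if addressed, for platelets as well as hemoglobin.
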